### **Overview of the Study Design:**

We propose to conduct a pilot intervention trial assessing the feasibility of decreasing the time to initiate TH for infants born in community hospitals who receive a Maine Neonatal Encephalopathy Teleconsult (Maine NET) compared 1:2 to with matched historical controls from the MMC database. We will also qualitatively assess provider experience of Maine NET (Appendix C) via zoom interviews and the parent perception of the process of having a telemedicine consult and participating in research in the setting of a critically ill newborn (Appendix D).

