**Human Subjects:**

Recruitment sites: Multiple community hospitals in Maine have been offered the opportunity to participate in this feasibility study and all centers have provided letters indicating a strong desire for participation. See site list for recruiting community hospitals.

Inclusion criteria: Infants in need of Maine NET will be identified by the “Time is Brain” poster (see Appendix A) that was created and distributed across the state to all newborn nurseries at community hospitals in 2016. This poster is in routine clinical use and is intended to assist in the identification of infants with symptoms of NE. Rather than having inexperienced providers at community sites examine inclusion criteria for TH and make a determination of eligibility, this poster uses a color scheme in which the green designation denotes characteristics of low-risk infants who are not in need of consultation, the yellow designation denotes characteristics of moderate risk infants who should have consultation and who may need transfer, and the red designation denotes characteristics of high risk infants who are critically ill and will benefit from immediate consultation and transfer to a tertiary care center. Infants included in this study will be born at a community hospital, will be in either the yellow or red category on the “Time is Brain” poster, will be younger than 6 hours of age at the time of the consultation. Infants in the historical control group will be selected from the MMC database and matched according to gender, gestational age, severity of presenting encephalopathy (mild, moderate or severe) and community site at which the infant was born. Matching will occur after the 35 Maine NET subjects have been treated with TH. Infants assessed by Maine NET who are not treated with TH will not be compared to the control group. The control subjects will be chosen by an investigator blinded to the time to initiate TH and outcome of the infants from the database. Infants used for historical controls must have a time of TH initiation recorded in the MMC Therapeutic Hypothermia database. Any parent of any neonate, whether treated with hypothermia or not, will be eligible to participate in an interview about their telemedicine and research experience.

Exclusion criteria: Infants older than 6 hours at the time Maine NET is requested and infants for whom TH is not an appropriate therapy (e.g. due to premature birth or moribund status) will be excluded.

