If a parent chooses not to participate, [name] will thank the family for considering and the standard of care consult will occur without employing telemedicine. The current standard of care for infants born in community hospitals is to have the provider attending the delivery (pediatrician or family medicine doctor) call the NICU at MMC to describe the cord gas parameters, the Apgar scores and the level of NE in the infant as well as any other clinically relevant data. The Neonatologist at MMC may suggest that the community provider "passively cool" the newborn per our standard guideline (see Appendix B) until the transport team arrives to make the actual determination of whether the infant will require TH treatment.

Compensation: Subjects will not be compensated for participation.

Follow-up plan: All subjects treated with TH will be offered routine neurological follow up at ages 3, 6 and 12 months per usual clinical routine after treatment with TH. These follow up visits are to insure maximization of early intervention services if they are needed. These follow up appointments are part of standard clinical care.

**Primary Outcome:** Hour of life in which TH is started. The “zero hour” for TH is recorded in the infant’s electronic medical record and refers to the time at which the infant starts the TH protocol.

**Secondary Outcomes:** Time at which passive cooling is initiated, temperatures recorded by the community hospital during passive cooling, in-hospital mortality, presence of seizures on electroencephalogram (EEG) and brain injury on MRI. The EEG is a routine part of the clinical care of an infant treated with TH and is applied for the 72 hours during TH. The PI is the person primarily responsible for interpreting the results of the EEG. The MRI is also part of the routine clinical care of infants treated with TH and is interpreted by a neuroradiologist who is unaware of the status of the infant regarding whether Maine NET was utilized.

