**Analysis:** Baseline differences in selected characteristics between infants assessed by Maine NET versus historical controls will be compared using Fisher’s exact tests for categorical variables and t-tests, or their non-parametric equivalents for continuous variables. The primary analysis will compare differences in the time to achieve TH between infants assessed by Maine NET versus historical controls using a t-test. For secondary outcomes of mortality, seizures on EEG, and brain injury on MRI, chi-square or Fisher’s exact test will be used for analysis of the frequency of these adverse outcomes.

**Potential limitations and contingencies:** Maine NET has been successfully locally implemented at MMC with 11 successful teleconsults already performed. There are IT and other challenges involved in implementing Maine NET at outside hospitals, but, as should be evident from the enthusiastic letters of support, these institutions are more than eager to have this level of assistance and will work collaboratively to resolve challenges. If for some reason the Maine

NET cannot happen, providers will always default to the standard of care which is a phone call for assistance with decision making.

**Potential Risks and Benefits:** When working with PHI identifiers, there is always a risk of loss of confidentiality. This risk will be minimized in this study through use of a HIPAA compliant RedCap system, limited password-protected access, and use of a Master List, which will remove all PHI identifiers from the data that is used for analysis. Interview recordings will be stored on encrypted flash drives and within the MaineHealth Protected file share folder, which only the study team has access to. All identifiers will be removed from interview transcription for analysis.

Potential benefits for this study include determining if telemedicine can reduce time to initiation of TH treatment in community hospitals as well as documenting parent and provider experience in participation in telehealth consults for neonatal encephalopathy.

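### The primary comparison with historical controls is an unadjusted t-test, and no adjustment is pre-specified for prognostic factors outside the four used for matching

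*Combined protocol and SAP*

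**What the plan says.** The Overview of the Study Design describes a pilot in which Maine NET infants are "compared 1:2 to with matched historical controls from the MMC database". Under Human Subjects (Inclusion criteria), controls are "matched according to gender, gestational age, severity of presenting encephalopathy (mild, moderate or severe) and community site at which the infant was born". Two further safeguards or restrictions appear there: "The control subjects will be chosen by an investigator blinded to the time to initiate TH and outcome of the infants from the database", and "Infants assessed by Maine NET who are not treated with TH will not be compared to the control group".

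The Analysis section gives the primary method in one sentence: "The primary analysis will compare differences in the time to achieve TH between infants assessed by Maine NET versus historical controls using a t-test". It contains no regression, stratified or paired analysis, and no sensitivity analysis. On baseline it says: "Baseline differences in selected characteristics between infants assessed by Maine NET versus historical controls will be compared using" Fisher's exact tests, t-tests or non-parametric equivalents. The characteristics are not named, and nothing is said about what follows from the result.

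The paragraph on standard care, under Informed consent, says that the community provider telephones the NICU "to describe the cord gas parameters, the Apgar scores and the level of NE in the infant". Of these three items, only the level of NE is a matching factor.

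**The concern.** The two groups are defined largely by era, so balance on prognostic factors comes only from matching. Four factors are matched and severity has three grades, so infants within a grade can still differ in how depressed they were at birth. That could affect how quickly an infant is recognised, called about and cooled. The Background makes a change in case mix over time plausible, since it links the growth in TH use to better recognition of mild to moderate NE.

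If an unmatched factor differs between groups and is related to age at TH start, the unadjusted difference mixes its effect with that of telemedicine. Baseline significance tests are a weak safeguard at this sample size. A non-significant result is not evidence of balance, and a significant one has no stated consequence. Study Goals puts first the question whether telemedicine reduces time to TH, so the primary estimate has to be interpretable.

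**Working it through.** **Inputs from the plan**
- 30 per group, 1 h difference, 95% power (Power calculation).
- 1:2 matching (Overview of the Study Design). With the 30 treated infants expected in the Power calculation this gives 30 v 60. The Inclusion criteria speak of 35 treated infants, which would give 35 v 70.

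**Assumed, because the plan does not state them**
- Two-sided 5% alpha.
- SD of time to TH, back-solved in step 1.
- One unmatched covariate with standardised imbalance *s* between groups and within-group correlation *r* with time to TH. Both are what remains after matching. No document gives either value.

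**Step 1. SD implied by the power statement.** With 30 per group (58 degrees of freedom), noncentral-t power of 95% needs a standardised difference of 0.947. So SD = 1/0.947 = 1.056 h. The 95% figure cannot be checked independently, because no SD or alpha is given.

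**Step 2. How often the baseline t-test flags an imbalance, 30 v 60.** Noncentrality = s / √(1/30 + 1/60) = s / 0.2236, with 88 degrees of freedom.

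| Imbalance s | Noncentrality | Probability of p < 0.05 |
|---|---|---|
| 0.2 SD | 0.89 | 14% |
| 0.3 SD | 1.34 | 26% |
| 0.5 SD | 2.24 | 60% |

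**Step 3. Shift and type I error of the unadjusted t-test with no true effect, 30 v 60.** Shift = r × s × SD. Standard error = 1.056 × 0.2236 = 0.236 h. Noncentrality = shift / 0.236.

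| s, r | Shift | Noncentrality | Type I error |
|---|---|---|---|
| 0.2, 0.2 | 0.2 × 0.2 × 1.056 = 0.04 h (2.5 min) | 0.18 | 5.4% |
| 0.3, 0.3 | 0.3 × 0.3 × 1.056 = 0.10 h (5.7 min) | 0.40 | 6.8% |
| 0.5, 0.5 | 0.5 × 0.5 × 1.056 = 0.26 h (16 min) | 1.12 | 20% |

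Shift and standard error both scale with the SD, so the error rates do not depend on it. The shifts do: at an SD of 2.0 h they would be 0.08, 0.18 and 0.50 h.

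**Step 4. What adjustment does in the last scenario.** In simulation (8,000 runs, 30 v 60, s = r = 0.5, no true effect), the unadjusted test rejected 20% of the time. Regression on group and the covariate had bias of about 0 and rejected about 5% of the time. The simulated confounder is linear, fully observed and measured without error, so this is a best case.

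**Step 5. Missing covariate values.** In the same scenario with 30% of covariate values missing at random in both groups (4,000 runs), a missing-indicator regression left 0.08 h of the 0.26 h bias.

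**The case against.** The existing control is substantial. Severity grade is the closest available proxy for how depressed an infant is, birth site captures much of the distance and transport element, and the blinded selector cannot choose controls by their timing. Only the part of cord gas or Apgar that is independent of these factors can confound. This stands as a reason to expect modest residual bias, and it makes the 0.5 and 0.5 scenario severe. It does not extend to factors outside the four.

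The study is also called a feasibility pilot. Even so, the Number of subjects paragraph justifies its enlargement partly by the need for statistical comparison with historical controls.

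Three stronger readings are tempting, and the documents do not support them:
- **That baseline differences will never be used.** The plan states no use for them. It does not rule out adjustment, and the unnamed characteristics may include cord gas and Apgar.
- **That the t-test will overstate the benefit of telemedicine.** The direction is unknown. If later-era treated infants are less depressed and recognised more slowly, the bias would run against telemedicine.
- **That adjustment would make the comparison sound.** Calendar period largely coincides with group, so regression on cord gas and Apgar cannot remove secular change in recognition or transport.

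**Conclusion.** The point holds as a gap in pre-specification. A non-randomised comparison is to be analysed by an unadjusted t-test, with no planned handling of factors outside the matching and no stated consequence of the baseline tests. Whether an imbalance will occur, and its size and direction, cannot be known from the documents.

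Under the assumed values the effect ranges from negligible (0.04 h, 5.4% type I error) to a quarter of the 1 h target (0.26 h, about 20%). Those figures rest on a back-solved SD, an assumed two-sided 5% alpha, 30 v 60 infants and a single linear confounder. They are illustrations, not predictions. The change is worth making because it is inexpensive and, if fixed before matching, prevents covariates from being chosen after the results are seen.

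**What to change.** In the Analysis section, before matching takes place:
1. Define the primary estimate as the group difference, with 95% CI, from a linear regression of age at TH start on group, the matching factors (or matched set, for example as a random intercept) and two named covariates: one cord gas measure and one Apgar score. Keep the t-test as a supportive analysis.
2. Handle missing covariate values by multiple imputation, not by a missing indicator.
3. Replace baseline p-values by standardised differences between TH-treated Maine NET infants and their controls, and name the characteristics.
4. State that adjustment does not remove calendar-time change.

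The cost is some SAP text and code, a few degrees of freedom (more if each birth site or matched set enters as a fixed effect), and abstraction of cord gas and Apgar values for the controls. The plan requires only that controls have a recorded TH start time, so the availability of these values must be confirmed before the covariates are fixed.

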**Title:** Telemedicine to Improve Use of Therapeutic Hypothermia in Rural Settings

**Clinicaltrials.gov #:** NCT03706417

[figure not shown]
**Background:** Neonatal Encephalopathy (NE) is a clinical syndrome affecting between 2-5 per 1000 live births. Abnormalities in the newborn neurological exam are the hallmark of NE which occurs due to the combined effects of lack of oxygen and blood flow to the brain around the time of birth. As many as 15-20% of infants with NE do not survive their brain injury and 25% of survivors experience substantial neuro-developmental deficits including intellectual disability, cerebral palsy, epilepsy and hearing or vision loss. Until recently, infants suspected of having NE were treated with supportive care alone as there were no known therapeutic interventions. Approximately ten years ago, however, treatment options dramatically changed with the introduction of therapeutic hypothermia (TH), a novel neuroprotective therapy which involves deliberately decreasing the infant's body temperature to 33.5°C for 72 hours. The early safety studies of TH were published in the late 1990's and the positive results of the first efficacy trials in 2005 moved this promising therapy into mainstream clinical practice. In a meta-analysis of 8 published clinical trials, TH was associated with a 25% decrease in the aggregated outcome of all-cause mortality and severe neurological abnormality and, as such, has become the standard of care for these critically ill infants.

Maine Medical Center (MMC), a tertiary care center with the only Neonatal Intensive Care unit (NICU) in the southern part of the state, employed TH for the first time in 2008.

Eastern Maine Medical Center (EMMC) is the only tertiary care center in the northern part of the state and began using TH in 2009. In 2012, a Neonatal Neurology Program was started at MMC and this program was extended to EMMC through a unique and unprecedented collaboration in 2013. At both institutions, the number of infants treated with TH gradually increased with improved recognition of the mild to

moderate forms of NE (Figure 1). While educational outreach efforts have successfully increased awareness of the symptoms of NE at both tertiary care centers in the state, infants who may benefit from TH are still not always recognized in a timely fashion. Missed

Figure1: Growth in use of Therapeutic Hypothermia (TH) at MMC and EMMC.

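### Brain injury on MRI is compared on its own beside mortality, with no handling of death before MRI, so a survival difference could modestly distort the MRI comparison

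*Combined protocol and SAP*

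**What the plan says.** The Secondary Outcomes paragraph lists, among others, "in-hospital mortality, presence of seizures on electroencephalogram (EEG) and brain injury on MRI". The Analysis paragraph tests each clinical outcome separately: "For secondary outcomes of mortality, seizures on EEG, and brain injury on MRI, chi-square or Fisher’s exact test will be used". What is compared is how often each event occurs, and no composite is defined.

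On how MRI is obtained, Secondary Outcomes says "The MRI is also part of the routine clinical care of infants treated with TH". It does not say when the scan is done. Of the EEG it says that it "is applied for the 72 hours during TH", which fixes the length of cooling but not the day of imaging. Nothing states the MRI denominator or what happens to an infant who dies unscanned.

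The Background gives the only mortality figure, for neonatal encephalopathy (NE) in general: "As many as 15-20% of infants with NE do not survive their brain injury". It also cites a meta-analysis of therapeutic hypothermia (TH) that combined death with neurological outcome and found "a 25% decrease in the aggregated outcome of all-cause mortality and severe neurological abnormality".

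**The concern.** An infant who dies before MRI has no MRI result, and the plan leaves two ways to treat that infant. If the infant leaves the denominator, the comparison is restricted to infants who survived to imaging, and survival is itself an outcome that the teleconsult may change. If the infant stays in as not injured, one of the worst outcomes counts as a good one.

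Either way, suppose earlier cooling saves some severely affected infants. They reach the scanner, many are injured, and the Maine NET injury rate rises although no infant did worse. If more Maine NET infants died, the rate could look better. The Background hypothesises better short-term outcomes, and MRI injury is one of the few clinical outcomes that bear on this. Because the controls are historical, a change in survival over time would act in the same way even if the teleconsult had no effect.

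**Working it through.** The plan states no figure for MRI injury or mortality in this comparison. Its one power figure concerns time to TH, so there is nothing to reproduce here.

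**Inputs from the documents**
- Group sizes: 30 TH-treated Maine NET infants (Power calculation) and, at the 1:2 ratio in Overview of the Study Design, 60 controls. The Human Subjects section also mentions 35 treated infants; the percentages below do not depend on which is used.
- Mortality: up to 15-20%, for NE in general (Background).
- Survivors with deficits: "25% of survivors experience substantial neuro-developmental deficits". This is a neurodevelopmental rate, used only as a stand-in for an MRI injury rate, which the documents do not give.

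**Assumptions**
- m_C and m_N: mortality in controls and in Maine NET.
- q: injury rate in infants who would survive in either group.
- r: probability of injury in infants who die in one or both groups (including those saved by Maine NET).
- f: share of deaths that precede MRI.
- Maine NET changes survival only.

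**Formulas**
- Controls, injured among imaged: [(1 − m_C)q + m_C(1 − f)r] / (1 − f·m_C)
- Maine NET, injured among imaged: [(1 − m_C)q + (m_C − m_N)r + m_N(1 − f)r] / (1 − f·m_N)
- Death or MRI injury, all treated infants: controls m_C + (1 − m_C)q; Maine NET m_N + (1 − m_C)q + (m_C − m_N)r

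**1. Strong case.** m_C = 20%, m_N = 10%, q = 25%, r = 1, f = 1.
- Controls: 12 of 60 die, 48 are imaged, 12/48 = 25.0% injured.
- Maine NET: 3 of 30 die, 27 are imaged, injured = 6 + 3 = 9, and 9/27 = 33.3%.
- False excess: +8.3 points. Fisher p = 0.59.
- Composite: (12 + 12)/60 = 40% v (3 + 9)/30 = 40%.
- If dead infants stay in as not injured: 12/60 = 20% v 9/30 = 30%, which misleads in the same direction.

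With q = 50% instead, the imaged rates are 24/48 = 50.0% v 15/27 = 55.6% (Fisher p = 0.81), and the composite is 36/60 v 18/30, both 60%.

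**2. Moderate cases.** 25% relative mortality reduction (m_N = 0.75·m_C), r = 1. Entries are Maine NET minus control, in percentage points, among imaged infants.

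| m_C | q | all deaths before MRI | half before MRI | none before MRI |
|---|---|---|---|---|
| 20% | 25% | +4.4 | +1.8 | 0 |
| 20% | 50% | +2.9 | +1.2 | 0 |
| 10% | 25% | +2.0 | +0.9 | 0 |
| 10% | 50% | +1.4 | +0.6 | 0 |

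First cell: (0.80 × 0.25 + 0.05)/0.85 = 29.4% v 25.0%.

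**3. Wider grid with better Maine NET survival.** m_C 10-20%, m_N 5-15%, q 25-40%, r 0.8-1.0: +2.1 to +11.8 points if all deaths precede MRI, and +1.0 to +5.1 if half do. The difference is zero if none do, or if mortality is equal. It is also zero with f = 1 and r = q, because the saved infants then resemble the other survivors.

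**4. A true MRI benefit can be masked.** As in step 1, but with injury in infants who would survive anyway falling from 25% to 20% under Maine NET: imaged infants show 25.0% v (0.80 × 0.20 + 0.10)/0.90 = 28.9%. The composite shows 40% v 0.10 + 0.26 = 36%, the right direction.

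**The case against.** The case against has several sound parts.

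- **The mechanism rests on unstated facts.** The documents do not say when MRI is done, how many infants die before it, or that mortality will differ. If most deaths follow imaging, little happens.
- **The mortality figure is an upper figure for NE in general.** The compared infants are all treated with TH, moribund infants are excluded, and mild encephalopathy is one of the matching levels. Mortality may well be lower.
- **Halving deaths is a lot to ask.** Both groups are cooled, and the power statement concerns a 1-hour earlier start. The Background credits TH itself with a 25% reduction in a combined outcome.
- **The distortion is small against the noise.** One infant among 27 is 3.7 points, and a reader would see mortality reported in the same analysis.
- **A composite has its own weakness.** In the strong case it shows 40% v 40% although deaths were halved. It also equates death with any MRI injury, since no severity threshold is given; the meta-analysis combined death with severe abnormality, so it is not an exact precedent.

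All of this stands as a limit on size and as an argument against replacing the MRI outcome or making mortality merely descriptive. It does not remove the gap: the plan still has no handling of death before MRI, and a pilot's secondary results are read for direction and size more than for p-values.

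A reader might infer that the MRI outcome will point the wrong way, or that 4.5 to 6 Maine NET infants (15-20% of 30) and 9 to 12 controls (15-20% of 60) will lack an MRI. The documents do not support either. Those counts need the NE-wide mortality to apply unchanged and every death to precede imaging.

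**Conclusion.** The point holds in a limited form. The plan compares MRI injury as a stand-alone frequency and does not handle death before imaging, so a survival difference can shift that comparison against the group that survives better. Three conditions are needed: some deaths before MRI, different mortality, and more frequent injury in the infants who make up that difference than in other survivors. The documents establish none of them and exclude none.

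Under the moderate assumptions the shift is about 1 to 5 points (0.6 to 4.4 in the table). Only stacked assumptions take it to 8 points or more. It would rarely be statistically significant at about 30 v 60 infants. Severity is low to moderate: the outcome is secondary, the study is a pilot, and the primary comparison of time to TH is not affected.

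**What to change.** In Secondary Outcomes and Analysis:

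1. Keep in-hospital mortality and MRI brain injury as listed and tested.
2. Add the outcome in-hospital death or brain injury on MRI, compared by chi-square or Fisher's exact test over TH-treated Maine NET infants and their matched controls.
3. Label the MRI-only comparison as being among imaged infants. Report by group the number not imaged, split into died before MRI and survived without MRI.
4. Show the composite with survivors without MRI excluded and, as sensitivity checks, with them counted as injured and as not injured.

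This should be settled before outcomes are compared.

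**Cost.** No new endpoint, visit or sample size is needed, since both components are already planned. The split of unscanned infants may take a record check for historical controls: the protocol requires only that their TH start time be in the database. The composite mixes events of different severity and can hide a survival gain, so mortality must always be shown beside it.

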\* Denotes partial year of data collection

opportunities for TH can occur when an infant's clinical presentation is less severe compared to those included in the original randomized controlled trials.

While TH must be initiated within the first 6 hours of life, there is solid evidence for improved outcomes in those for whom TH is initiated earlier. As a result of exceptional preclinical animal models of NE in the fetal lamb and piglet, there is a robust biochemical understanding of the temporal evolution of brain injury in neonates. TH must be initiated prior to 6 hours of life to intercede upon the second stage of injury with its features of excitotoxicity and associated cascade of inflammatory mediators that cause seizures and ultimately cell death. Animal models have demonstrated lack of neuronal rescue if TH is initiated late (8.5 hours after ischemic insult) and have also demonstrated improved neuronal rescue with earlier initiation of TH at less than 3 hours. In a prospective cohort study, infants treated with TH prior to three hours of life were found to have improved motor function compared to those whose treatment was initiated after 3 hours. In one of the first clinical trials of TH, the relative risk of death or severe abnormal neurological outcome was decreased in those for whom TH was started before 4 hours of life. This combination of animal and human data suggests that mechanisms to improve the rapid initiation of TH, such as through a teleconsult, may lead to improved outcomes for infants with NE. In the proposed study, we hypothesize that use of telemedicine consults between a tertiary care center and a community hospital can improve the assessment, management, and short-term outcomes of infants with NE by decreasing delay in the initiation of TH through rapid and accurate assessment of NE.

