Number of subjects: We intend to recruit a total of 125 infants from the participating centers. Each center has referred between 0 and 6 infants for TH annually for the past 4 years and, by involving this number centers, it is likely that the targeted goal of 125 study subjects is achievable (Table 1). We have increased the number from 10 to 20 and then to 40 and then to 100 due to the fact that not all recruited infants will be treated with TH and to have an adequate sample size to make statistical comparisons with historical controls. We anticipate that by recruiting 125 infants we will be able to analyze data in the best way possible. We will recruit no more than 30 parents for the interviews.

Power calculation: With new funding from the COBRE grant, this study has expanded to recruit 125 subjects of whom we expect 30 to have been treated with hypothermia. 30 subjects in each group would yield 95% power to detect a 1hour difference in time to initiate TH.

Informed consent: Prior to the onset of any research related activities, informed consent for the main study will be obtained from one of the infant's parents through the telehealth interface. A paper copy of the informed consent document (ICF) will be provided to the parent and will be described in full detail by [name] who will answer all the parent's questions thoroughly. The parent will then sign and date and time the ICF document if they wish to have their infant participate. Parents will be asked to initial the informed consent document if they wish to be contacted about participation in the parent interview portion of the project. The physician at the participating hospital will witness the parent signature and also sign, date and time the ICF on the witness line. [name] will then sign a separate copy of the ICF and date and time it as well. The consent form that the parent signed will be transported with the baby to MMC or faxed to MMC by providers from the community hospital and will be conjoined with the copy signed by [name] and then uploaded into the infant's electronic medical record.

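### Mortality, EEG seizures and MRI injury are analysed only by significance tests at about 30 v 60, with no effect estimate or interval, although improved short-term outcomes are part of the hypothesis

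*Combined protocol and SAP*

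**What the plan says.** The hypothesis at the end of the Background is that telemedicine consults "can improve the assessment, management, and short-term outcomes of infants with NE", through earlier initiation of therapeutic hypothermia (TH). Secondary Outcomes lists in-hospital mortality, seizures on EEG and brain injury on MRI among its items. For these three, the Analysis paragraph gives one instruction: a chi-square or Fisher's exact test "will be used for analysis of the frequency of these adverse outcomes". It names no risk difference or ratio, no confidence interval and no rule for reading a non-significant result.

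The numbers compared are small. Under Inclusion criteria, "Infants assessed by Maine NET who are not treated with TH will not be compared to the control group". The Power calculation paragraph plans 125 recruits, "of whom we expect 30 to have been treated with hypothermia", and the Overview has them "compared 1:2 to with matched historical controls from the MMC database". That gives about 30 v 60. Inclusion criteria has a different count ("Matching will occur after the 35 Maine NET subjects have been treated with TH"), which would give 35 v 70. The only power statement concerns time to initiate TH.

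**The concern.** One part of the hypothesis concerns clinical outcomes, and the only planned output for that part is a p-value. With 30 and 60 infants and outcomes such as death, a p-value says little about which effects the data rule out. If it is above 0.05 and stands alone, a reader may conclude that telemedicine made no difference to death, seizures or brain injury, when the data may be compatible with a worthwhile benefit or a serious harm. A pilot is most useful to a later study for its estimates and their precision, and the analysis text does not ask for them.

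**Working it through.** **The plan's own power figure.** The Power calculation paragraph states 95% power for a 1-hour difference with 30 per group. It gives no SD, alpha or sidedness, so the figure cannot be reproduced. At two-sided 5% it is attainable if the SD is about 1.06 hours (t-test). It concerns the primary outcome only. No corresponding figure exists for mortality, seizures or MRI injury.

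**Inputs**
- Group sizes: 30 v 60 (Power calculation, Overview); 35 v 70 as sensitivity (Inclusion criteria).
- Mortality: the only rate given is in the Background ("As many as 15-20% of infants with NE do not survive their brain injury"). It describes infants with NE generally and is used here as an assumption.
- Effect: the only relative effect given is also in the Background ("TH was associated with a 25% decrease in the aggregated outcome of all-cause mortality and severe neurological abnormality"). It is for TH and for a composite. Here both groups receive TH and differ in its timing, and the figure is applied to mortality alone. It too is an assumption.
- Seizure and MRI injury rates: not stated. Control rates of 30%, 40% and 50% are assumed.
- Two-sided 5% (not stated). Arms treated as independent, so matching is ignored.

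**Power.** With p the control rate and r the rate ratio, sum Binomial(30, rp) × Binomial(60, p) over all tables for which the test gives p ≤ 0.05. The chi-square is without continuity correction.

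| Deaths, control to Maine NET | Fisher | Chi-square |
|---|---|---|
| 15% to 11.25% (25% reduction) | 4.2% | 6.5% |
| 20% to 15% (25% reduction) | 5.9% | 7.8% |
| 15% to 7.5% (halving) | 10.1% | 14.4% |
| 20% to 10% (halving) | 15.9% | 20.3% |
| 15% to 30% (doubling) | 34% | 40% |
| 20% to 40% (doubling) | 47% | 52% |

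With a continuity correction, the two 25%-reduction rows fall to 2.2% and 3.3%. At 35 v 70 they are 5.1% and 6.9% by Fisher, and 6.1% and 8.1% by uncorrected chi-square, so the 30/35 discrepancy does not matter here.

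| Assumed control rate, seizures or MRI injury | Fisher, 25% reduction | Fisher, halving |
|---|---|---|
| 30% | 9.1% | 30.8% |
| 40% | 12.1% | 43.0% |
| 50% | 18.2% | 60.3% |

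**Precision.** Half-width of the 95% interval for a risk difference = 1.96 × √[p₁(1−p₁)/30 + p₂(1−p₂)/60], with p₁ = 0.75p₂.
- p₂ = 0.15: 1.96 × √(0.003328 + 0.002125) = 0.145
- p₂ = 0.20: 1.96 × √(0.004250 + 0.002667) = 0.163
- p₂ = 0.30: 1.96 × √(0.005813 + 0.003500) = 0.189
- p₂ = 0.50: 1.96 × √(0.007813 + 0.004167) = 0.215

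For mortality, the assumed differences are 3.75 and 5 points, against half-widths of 14.5 and 16.3 points.

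**Illustration.** With 3/30 v 9/60 deaths, Fisher's p = 0.74. The observed difference is 5 points fewer deaths, and the Newcombe 95% interval runs from 18 points fewer to 12 points more. The p-value alone conveys none of this.

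**The case against.** The strongest reply is that the plan does not overclaim. The Overview calls the study a pilot of the feasibility of shortening time to TH. The outcomes are secondary, the only power claim is for time to TH, and the Study Goals do not mention mortality, seizures or MRI injury. Low power for such outcomes is normal in a pilot. Nothing says that a non-significant result will be read as no effect, and reported frequencies with denominators would let a reader compute an interval. All of this stands. It makes the matter one of presentation and leaves the primary analysis untouched. It does not supply the missing estimates, and it does not explain why significance tests should be the only analysis named for these outcomes.

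A reader might infer several stronger things that the documents do not support:
- That the result will be non-significant whether telemedicine helps, does nothing or harms. A doubling of deaths would be detected 34-47% of the time by Fisher's test.
- That a null is foregone for all three outcomes. No seizure or MRI injury rates are given, and at the assumed rates a halving is detected 31-60% of the time.
- That the test never exceeds its nominal error rate at a 25% reduction in deaths. The values straddle 5%.
- That the trial was designed around 15-20% mortality and a 25% reduction. Those are background literature figures. An earlier start of TH may well have a smaller effect than TH itself, but the documents give no size for it.

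**Conclusion.** The point holds as a minor improvement to the analysis text. The plan includes short-term outcomes in its hypothesis but analyses death, seizures and MRI injury by significance test alone. On the borrowed background figures, power for mortality is about 4-8% for a 25% reduction and 10-20% for a halving, across Fisher and uncorrected chi-square. For seizures and MRI injury, power is low but not nil, and it depends on rates the documents do not give. A non-significant result would leave effects of roughly 14-16 points (mortality) or 19-21 points (the others) either side of the observed difference unexcluded. These figures assume two-sided 5%, 30 v 60 and independent arms. That such a result would mislead is a risk the text does not guard against; the documents do not plan for that reading.

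**What to change.** In the Analysis paragraph, for each of the three outcomes, report the frequency in each group and the risk difference with a small-sample 95% confidence interval. Either use a method that allows for the 1:2 matching, or use an independent-groups method such as Newcombe and state that matching is ignored. Label these outcomes exploratory, and state that an interval including zero is not evidence of no effect. The chi-square or Fisher tests may stay as supplementary.

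In the Background, state that time to TH is the tested hypothesis and that short-term outcomes are estimated.

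The cost is a wording change and trivial extra analysis, with no more patients. The one downside is that the study no longer claims to test short-term outcomes.
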